#### 15.4 Efficacy Analysis

Response to treatment will be evaluated using RECIST v1.1 for patients with solid tumors (except for mesothelioma; [Eisenhauer 2009](#)). For patients with pleural mesothelioma, response will be evaluated using the modified RECIST criteria for pleural mesothelioma ([Byrne 2004, Attachment 5](#)). Responses for patients with pericardial or peritoneal mesothelioma will be described based upon RECIST v1.1 for patients with measurable disease combined with clinical improvements.

The Kaplan-Meier method will be used to estimate the median Duration of Response (DOR) and Progression-Free Survival (PFS) for each treatment cohort in Dose Expansion (note: Dose Escalation patients of the same histology enrolled at the RP2D will be included in this analysis). Efficacy analyses will be performed on the Efficacy Evaluable Population. Additional efficacy analyses will also be performed on an expanded population that includes patients that lack post-treatment scans due to toxicity or death.

For each patient with objectively measurable disease, response to therapy, will be calculated using RECIST v1.1 and Modified RECIST for pleural mesothelioma (DOR, PFS, Best Overall Response [BOR], and Overall Response Rate[ORR]).

- DOR is defined as the number of days from the date of initial response (PR or better) to the date of first documented disease progression/relapse or death, whichever occurs first.
- PFS is defined as the number of days from the date of treatment initiation (i.e., C1D1) to the date of documented disease progression or death from any cause, whichever occurs first, and will be calculated for all patients. In the event that no disease progression or death is documented prior to study termination, analysis cutoff, or the start of confounding anticancer therapy, these endpoints will be censored at the date of last available tumor assessment.

- BOR is the best RECIST v1.1 /modified RECIST for pleural mesothelioma response recorded from the start of the study treatment until disease progression/recurrence.
- ORR is defined as the response of the proportion of efficacy evaluable patients with tumor size reduction from the time the start of treatment until documented tumor progression. ORR includes complete response (CR) and partial response (PR).

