Part 1b is a standard 3+3 dose escalation design. Upon opening Part 1b, a minimum of 3 patients will receive pembrolizumab (200 mg IV Q3W) in combination with INCB001158. Enrollment in Part 1b is limited to patients with tumor types that would be eligible for the Expansion Cohorts in Part 3. In Part 1b, the starting dose of INCB001158 will be 50 mg BID, which is 2 dose levels below the recommended monotherapy Phase 2 dose of 100 mg BID identified in Part 1a of this study. Dose escalation will proceed according to the Dose Escalation Schedule that is being employed in Part 1a in the table below. A dose level shall not be enrolled in Part 1b until it has been demonstrated to be at or below the monotherapy MTD in Part 1a.

INCB001158 Dose Levels			
Cohort	BID Dose (mg)	% Increase	N
-1	25	- 50%	3 – 6
1*	50	-	3 – 6
1.5	75	50%	3 – 6
2	100	33%	3 – 6
3	150	50%	3 – 6
4	225	50%	3 – 6
5	300	33%	3 – 6
6	400	33%	3 – 6
7	500	25%	3 – 6
8	600	20%	3 – 6

\*starting dose level

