Upon opening Part 1b, a minimum of 3 patients will receive pembrolizumab (200 mg IV Q3W) in combination with INCB001158. Enrollment in Part 1b is limited to patients that would be eligible for the Expansion Cohorts in Part 3. In Part 1b, the starting dose of INCB001158 will be 50 mg BID, which is 2 dose levels below the recommended monotherapy Phase 2 dose of 100 mg BID identified in Part 1a of this study. Dose escalation will proceed according to the Dose Escalation Schedule that is being employed in Part 1a (Table 5.1-1). A dose level shall not be enrolled in Part 1b until it has been demonstrated to be at or below the monotherapy MTD in Part 1a.

*Part 1c. INCB001158 in Combination with Pembrolizumab in Patients with Moderately Impaired Renal Function*

At US sites only, Cohort 1c will enroll 6 patients who have moderately impaired renal function (defined as CrCl 30-49 mL/min calculated by the Cockcroft-Gault formula) AND meet eligibility criteria for any of the combination expansion cohorts (3a through 3h). The safety of INCB001158 in combination with pembrolizumab was fully characterized with a comprehensive dose escalation in patients with CrCl  $\geq 50$  mL/min. Additionally, pembrolizumab did not have

any effect on the PK of INCB001158. Therefore, Cohort 1c will evaluate a reduced dose of INCB001158 50 mg BID (determined using population PK modeling) in combination with pembrolizumab in order to determine a pharmacodynamically active dose in patients with moderately impaired renal function.

Based on population PK modeling, a dose of INCB001158 50 mg BID in patients with CrCl 30 to 49 mL/min is predicted to achieve INCB001158 AUC/Cmin values to fall within the known safe exposure range corresponding to doses at the established RP2D of 100 mg BID (see Section 10.2). Six patients meeting eligibility criteria for Parts 3a through 3h will be enrolled at the reduced dose of 50 mg BID to obtain full PK, PD (see Attachment 2C), and safety data. All data collected during the first cycle (21 days) will be evaluated, along with the population PK modeling data, to determine the INCB001158 dose in patients with moderately impaired renal function that most closely approximates the PK parameters of the RP2D of 100 mg BID in patients with normal renal function and specifically meets the following PK and PD criteria:

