**Part 1b: Inclusion Criteria Specific to the PD-1 Combination Dose Escalation**

1. Histologically or cytologically proven diagnosis of advanced/metastatic NSCLC (squamous or non-squamous), mesothelioma, gastric/GEJ cancer, MSS CRC, MSI-H CRC, UCC, melanoma or SCCHN in patients who have disease progression after treatment with all available therapies known to confer clinical benefit. Patients that have not received prior anti-PD-1 therapies are allowed.

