**Part 2d:**

1. Meets the criteria for any of Parts 2a, 2b, or 2c.
2. [REDACTED]

***Part 3: Inclusion Criteria Specific to the PD-1 Combination Cohort Expansion*****Part 3a: Non-small cell lung cancer (NSCLC) – PD/SD on anti-PD-1/PD-L1 therapy**

1. Histological or cytological diagnosis of locally advanced unresectable or metastatic NSCLC that does not harbor an activating EGFR or ALK mutation
2. Prior progression on or after platinum-based chemotherapy or refused/ineligible to receive platinum-based chemotherapy.
3. Received an anti-PD-1/PD-L1 agent in a prior line of therapy for advanced/metastatic disease and EITHER:
  - a. Had documented radiological disease progression (per Investigator assessment, preferably with confirmation of PD after 4 weeks) while receiving anti-PD-1/PD-L1 therapy in the most recent line of therapy, OR
  - b. Had documented stable disease (per Investigator assessment) for  $\geq 24$  weeks while receiving pembrolizumab therapy in the most recent line of therapy

Part 3b: Melanoma – PD/SD on anti-PD-1/PD-L1 therapy

1. Histological or cytological diagnosis of locally advanced unresectable or metastatic melanoma
2. Received an anti-PD-1/PD-L1 agent in the most recent prior line of therapy for advanced/metastatic disease and EITHER:
  - a. Had documented radiological disease progression (per Investigator assessment, preferably with confirmation of PD after 4 weeks) while receiving anti-PD-1/PD-L1 therapy in the most recent line of therapy, OR
  - b. Had documented stable disease (per Investigator assessment) for  $\geq 24$  weeks while receiving pembrolizumab therapy in the most recent line of therapy

Part 3c: Urothelial cell carcinoma (UCC) – PD/SD on anti-PD-1/PD-L1 therapy

1. Histological or cytological diagnosis of locally advanced unresectable or metastatic UCC
2. Received an anti-PD-1/PD-L1 agent in the most recent prior line of therapy for advanced/metastatic disease and EITHER:
  - a. Had documented radiological disease progression (per Investigator assessment, preferably with confirmation of PD after 4 weeks) while receiving anti-PD-1/PD-L1 therapy in the most recent line of therapy, OR
  - b. Had documented stable disease (per Investigator assessment) for  $\geq 24$  weeks while receiving pembrolizumab therapy in the most recent line of therapy

Part 3d: Mismatch repair deficient and/or microsatellite instability-high (MSI-H) colorectal cancer (CRC) – PD/SD on anti-PD-1/PD-L1 therapy

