***Part 3*****Part 3a: NSCLC**

1. Documented activating mutations in EGFR or ALK.

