### 10.2.3.2 Combination with Anti-PD-1 (Pembrolizumab)

As of the date when this amendment was authored, the anti-PD-1 agent pembrolizumab has been approved for the treatment of metastatic melanoma, NSCLC, SCCHN, urothelial carcinoma, and solid tumors that are microsatellite instability-high (MSI-H) or mismatch repair deficient (dMMR). Despite the impressive activity observed for this and other anti-PD-1/PD-L1 agents, a majority of patients with these diseases do not achieve an objective response to these agents and there is a recognized need for combination agents to either expand the population that benefits or amplifies the activity that they provide (Melero 2015).

Eight patient populations are eligible to enroll into expansion cohorts, including advanced/metastatic NSCLC (Part 3a), advanced/metastatic melanoma (Part 3b), advanced/metastatic UCC (Part 3c), advanced/metastatic MSI-H CRC (Part 3d), advanced/metastatic MSS CRC (Part 3e), advanced/metastatic gastric /GEJ (Part 3f), advanced/metastatic SCCHN (Part 3g), and advanced/metastatic malignant pleural mesothelioma (Part 3h). Since a primary objective of the expansion cohorts is to identify a signal of clinical activity of INCB001158 in combination with pembrolizumab, some of these cohorts will enroll patients that are unlikely to respond to monotherapy pembrolizumab because they either 1) had disease progression (even after an objective response) in the immediate prior line of therapy, OR 2) had prolonged stable disease ( $\geq 24$  weeks) in the immediate prior line of therapy. The attribution of evidence of clinical activity (e.g., objective responses) to INCB001158 in this population can be made more confidently given the low likelihood of a response to monotherapy anti-PD-1 therapy. In addition to these “add-on” cohorts, other cohorts will enroll patients that have never received prior checkpoint inhibitor therapy. There are generally two reasons to include these cohorts: 1) to identify activity in patient populations that are known to be unresponsive to PD-1 therapy (e.g., MSS CRC) and 2) to identify activity of the INCB001158/pembrolizumab combination that could be missed in pembrolizumab-refractory patients.

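### The Protocol 15.4 pooling rule matches escalation patients to expansion cohorts on histology and RP2D but not on prior checkpoint exposure, so patients outside a Part 3 cohort's definition can enter its DOR and PFS; the SAP tables do otherwise without declaring a change

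*Protocol*

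**What the plan says.** Protocol 15.4 plans this: "The Kaplan-Meier method will be used to estimate the median Duration of Response (DOR) and Progression-Free Survival (PFS) for each treatment cohort in Dose Expansion". A note in the same sentence adds that "Dose Escalation patients of the same histology enrolled at the RP2D will be included in this analysis". Histology and dose are the only two conditions.

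The Part 3 cohorts are defined by more than histology (Protocol 7.1 and 7.2):

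- Cohorts 3b-3d use the criterion "Received an anti-PD-1/PD-L1 agent in the most recent prior line of therapy for advanced/metastatic disease and EITHER", completed by either radiological progression on that therapy or at least 24 weeks of stable disease on pembrolizumab. Cohort 3a has an equivalent requirement and also excludes "Documented activating mutations in EGFR or ALK".
- Cohorts 3e-3h require the reverse: no earlier checkpoint inhibitor.
- Cohorts 3d and 3e are both colorectal cancer and are separated by MSI status.

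The protocol describes entry to Part 1b in three ways:

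- Section 5.1: "Enrollment in Part 1b is limited to patients that would be eligible for the Expansion Cohorts in Part 3".
- Synopsis: "Enrollment in Part 1b is limited to patients with tumor types that would be eligible for the Expansion Cohorts in Part 3".
- Section 7.1, after listing all eight Part 3 tumor types and requiring progression after all available beneficial therapies: "Patients that have not received prior anti-PD-1 therapies are allowed". It sets no EGFR/ALK limit.

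The SAP has no pooling rule for Part 1b. SAP 5.1 describes efficacy displays for Parts 1a and 1b by dose level and for Parts 2 and 3 by tumor type, and adds only Part 1c to Part 3. Appendix A follows this. Part 1b has its own DOR tables (2.1.1.2.2, 2.1.1.4.2) and PFS table (2.1.2.2), and the Part 3 tables cover Part 1c plus Part 3. SAP 9.1 lists no changes to the protocol-defined analyses.

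**The concern.** The study has no control arm. For the add-on cohorts 3a-3d, Protocol 10.2.3.2 argues that "The attribution of evidence of clinical activity (e.g., objective responses) to INCB001158 in this population can be made more confidently", because a response to anti-PD-1 alone is unlikely after progression or prolonged stable disease on such therapy. That argument depends on prior treatment, which histology does not carry. A checkpoint-naive melanoma patient from Part 1b at the RP2D satisfies the 15.4 rule for 3b but lacks the feature that makes 3b interpretable. Such a patient may respond to pembrolizumab itself, which would tend to push DOR and PFS upward.

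The rule also works in other directions. Pretreated Part 1b patients could join 3e-3h and dilute them. An EGFR- or ALK-mutant NSCLC patient could join 3a, probably with a downward effect, since Protocol 5.3 calls such patients less responsive to anti-PD-1. If histology is read simply as colorectal cancer, the rule does not keep 3d and 3e apart.

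At stake is whether a cohort's DOR and PFS describe the population named in its title, and whether the protocol and SAP describe the same analysis.

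**Working it through.** **Does the rule have patients to act on?** Yes. Protocol 10.2.2.1 gives the combination RP2D as 100 mg BID and lists it among the dose levels tested in Part 1b.

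**How many?** Protocol 5.1 allows 3-6 patients per dose level plus up to 6 backfill, and Section 6.0 plans on a maximum of 12. Those 12 are spread over eight tumor types. The number who are checkpoint-naive and of a 3a-3d tumor type is not given. Call it k, with range 0 to 12; 12 would need the whole dose level to be naive and of one tumor type.

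**The plan's own design figure.** For 3a-3d (n1 = 11, r1 = 0; n = 26, r = 1), the probability of rejecting is the sum over x > 0 of P(X1 = x) × P(X2 ≥ 2 − x), with X1 ~ Bin(11, p) and X2 ~ Bin(15, p). This gives 0.804 at p = 15%, matching the stated 80% power, and 0.067 at p = 2%, inside the 0.1 limit. The 15.4 note concerns DOR and PFS only and leaves this test alone.

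**DOR, illustrated.** Inputs: N = 26 (both stages) or 11 (stopped at Stage 1); background ORR 2% (Protocol Table 15.2-1); naive ORR q assumed to be 20%, borrowed from the background rate for checkpoint-naive cohort 3g, a different tumor type.

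Naive share of patients = k / (N + k). Naive share of expected responders = kq / (0.02N + kq).

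| k | N = 26: patients | N = 26: responders | N = 11: patients | N = 11: responders |
|---|---|---|---|---|
| 1 | 4% | 0.2/0.72 = 28% | 8% | 0.2/0.42 = 48% |
| 3 | 10% | 0.6/1.12 = 54% | 21% | 0.6/0.82 = 73% |
| 6 | 19% | 1.2/1.72 = 70% | 35% | 1.2/1.42 = 85% |
| 12 | 32% | 2.4/2.92 = 82% | 52% | 2.4/2.62 = 92% |

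For k = 3 and N = 26, the responder share is 37% at q = 10% and 70% at q = 40%. These shares are large because the background rate yields only 26 × 0.02 = 0.52 expected cohort responders. At the 15% target rate, the cohort expects 26 × 0.15 = 3.9, and the share for k = 3, q = 20% falls to 0.6 / (3.9 + 0.6) = 13%. A cohort that just succeeds has 2 responders, so one added naive responder would be 1/3 of its DOR sample.

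**PFS, illustrated.** Take exponential PFS with cohort median 1 and an assumed naive median of 2. With w = k / (N + k), solve (1 − w)·2^(−m) + w·2^(−m/2) = 0.5 for the pooled median m. For N = 26, m rises by about 2% (k = 1), 7% (k = 3), 12% (k = 6) and 22% (k = 12). For N = 11 the rises are about 5%, 14%, 25% and 41%.

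**The case against.** The strongest reply is that no planned table would show the mixing, because Appendix A tables Part 1b apart from Part 3. That stands for the tables. It does not settle the matter, for four reasons. SAP 5.1 words the split permissively. Appendix A calls its lists guidelines. SAP 7.3.4 and 7.3.6 draw Kaplan-Meier curves by treatment group, and SAP Table 2 gives Parts 1b and 3 the same group name. SAP 9.1 declares no departure from the protocol, so the 15.4 rule has not been withdrawn.

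Second, Section 5.1 read literally keeps naive patients of the 3a-3d tumor types out of Part 1b. The Section 7.1 allowance could be meant for the tumor types of 3e-3h, whose cohorts require naive patients. The requirement for progression after all beneficial therapies, together with the pembrolizumab approvals listed in Section 10.2.3.2, should also make naive patients of the 3a-3d types uncommon. This stands to the extent that entry is possible, not established. But Section 7.1 states its allowance without limiting it by tumor type, and the synopsis limits by tumor type only.

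Third, DOR and PFS are secondary, all analyses are exploratory (SAP 3.2), and the attribution passage cites objective responses as its example. SAP 7.3.4 also withholds Kaplan-Meier DOR when responders are very few. Cohorts 3a-3d include patients with prolonged stable disease on pembrolizumab, so their PFS already carries some pembrolizumab effect. All of this limits the consequence without making histology an adequate matching rule.

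Fourth, MSI-H and MSS disease are listed as separate diagnoses in Section 7.1, so mixing 3d with 3e depends on a narrow reading of histology. That is fair; the word is undefined.

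**Conclusion.** The point holds as a gap in the protocol's pooling rule and an undeclared difference between protocol and SAP. Under 15.4 as written, checkpoint-naive Part 1b patients can enter the DOR and PFS of 3a-3d, and pretreated patients can enter those of 3e-3h. DOR is the more exposed. With a few naive patients the PFS shift is modest: about 2% to 7% for k = 1 to 3 with N = 26, even with a doubled naive median. The values of k, the naive response rate and the median ratio are assumptions; the documents give none of them.

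A reader might infer more, and the documents do not support it:

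- That naive patients do enter 3a-3d: Section 5.1 would bar them and no count is given.
- That the Simon decisions are compromised: the 15.4 note does not cover them.
- That the reported tables will be mixed: the planned tables keep Part 1b separate.
- That 12 naive patients in one cohort is a realistic figure: it is an extreme. At the 23 May 2018 cut, with escalation still under way, Part 1b held 21 patients in all (Protocol 10.1.9).

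The correction is worth making because it is cheap and the two documents currently disagree.

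**What to change.** Choose one of two routes:

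1. Delete the pooling note from Protocol 15.4, in line with the SAP tables, and record the change in SAP 9.1.
2. Keep pooling, but limit it to RP2D escalation patients who meet the cohort's own criteria on prior checkpoint therapy, MSI/MSS status and, for 3a, EGFR/ALK status. Show all other Part 1b patients only in the Part 1b displays, and align the SAP.

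Pooling wording belongs in SAP 7.3.4 and 7.3.6 only under the second route; those sections contain none now. State in the SAP that the Kaplan-Meier DOR and PFS figures keep Part 1b apart from Part 3, apart from any patients pooled under the second route. Reconcile the synopsis, Section 5.1 and Section 7.1 on who may enter Part 1b.

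The cost is wording. Prior therapy, MSI/dMMR and mutation status are already planned SAP outputs (SAP 6.1.2, 6.1.3), so no new data are needed. The downside is a few patients fewer in some cohort curves.

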7.3.4. Duration of Response

For objective responders, the DOR is the time from the first overall response contributing to an objective response to the earlier of the participant's death or first overall response of PD as assessed by RECIST v1.1 occurring after the first overall response contributing to the objective response. Partial death dates will be handled using the rules described in Section 4.1.4. Censoring of DOR will follow the same algorithm as the censoring of PFS (see Section 7.3.6).

Kaplan-Meier curves for DOR based on both unconfirmed and confirmed responses will be presented by treatment group. The Kaplan-Meier estimate of median DOR will be presented with its 95% CI. The 95% CI will be calculated using the generalization of Brookmeyer and Crowley's method (1982) with log-log transformation (Klein and Moeschberger 1997).

Duration of response analyses will only include responders, and any Kaplan-Meier analyses will only be provided if appropriate. For example, if there are a very small number of responders, Kaplan-Meier analysis will not be provided.

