7.3.5. Largest Percentage Reduction in Sum of Diameters of Target Lesions

For each participant in the FAS with target lesions at baseline, target lesion sizes will be measured by the sum of the diameters. The best percent change from baseline, defined as the largest decrease in target lesion size for each participant, will be summarized descriptively, and a waterfall plot of the best percent change will be generated. Note that for participants who only have increases in target lesion sizes from baseline, the smallest increase will be considered as the best change from baseline.

Per RECIST v1.1 criteria, target lesions considered "too small to measure" will be assigned a default value of 5 mm for purposes of this analysis. Likewise, target lesions identified as "not present" at postbaseline assessments will be assigned 0 mm for this analysis. In the event a target lesion is unaccounted for in a particular postbaseline timepoint (ie, assessment missing or NE), then the overall sum of diameters for target lesions will not be evaluable for that postbaseline timepoint.

7.3.6. **Progression-Free Survival**

Progression-free survival is defined as the length of time between the date of first dose and the earlier of death or PD as assessed by RECIST v1.1 per investigator assessment. Partial death dates will be handled using the rules described in Section 4.1.4. Censoring for PFS will follow the algorithm outlined in Table 4, which is based on FDA guidance (FDA 2015, FDA 2018).

Situation	Outcome	Date of Progression or Censoring
No baseline tumor assessments	Censored	Day 1
No valid postbaseline response assessments	Censored	Day 1
Progression documented between scheduled response assessments	Progressed	Date of first overall response of PD
No progression	Censored	Date of last valid radiologic assessment (not NE and not missing)
Study discontinuation for undocumented progression	Censored	Date of last valid radiologic assessment (not NE and not missing)
Study discontinuation for toxicity or other reason	Censored	Date of last valid radiologic assessment (not NE and not missing)
New anticancer treatment started	Censored	Date of last valid radiologic assessment (not NE and not missing) on/before starting a new anticancer treatment
Death before first progressive response assessment	Progressed	Date of death
Death between adequate response assessments	Progressed	Date of death

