Death or progression after 2 or more missed assessments	Censored	Date of last valid radiologic assessment (not NE and not missing)

Table 4:Evaluation and Censoring of Progression-Free Survival

Kaplan-Meier curves for PFS will be presented by treatment groups. The Kaplan-Meier estimate of median PFS will be presented with its 95% CI. The 95% CI will be calculated using the generalization of Brookmeyer and Crowley's method (1982) with log-log transformation (Klein and Moeschberger 1997).

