9.1. Changes to Protocol-Defined Analyses

Not applicable.

QTcF

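### Protocol 15.4 counts progression or death after two missed scans as a PFS and DOR event, SAP Table 4 censors it, and SAP 9.1 declares no change

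*Protocol*

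**What the plan says.** **Protocol, Section 15.4.** PFS runs from treatment initiation to "documented disease progression or death from any cause, whichever occurs first, and will be calculated for all patients". DOR runs from the initial response "to the date of first documented disease progression/relapse or death, whichever occurs first". One censoring clause follows. It applies only where neither event has been recorded by the time the study ends, the data are cut off or a confounding cancer treatment begins. For such patients, the protocol says that "these endpoints will be censored at the date of last available tumor assessment". The clause sits under PFS but refers to endpoints in the plural. Nothing in the section mentions missed assessments.

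**SAP, Section 7.3.6, Table 4.** The table lists "Death or progression after 2 or more missed assessments" with the outcome censored, dated at the last valid radiologic assessment. The SAP attributes the table to FDA guidance.

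**SAP, Section 7.3.4.** "Censoring of DOR will follow the same algorithm as the censoring of PFS", so the missed-scan rule also governs DOR.

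**SAP, Section 9.** Under "9.1. Changes to Protocol-Defined Analyses" the entry is that nothing applies. SAP Section 2.1 states that the plan is based on Protocol Amendment 2-US 3, which is the version of the protocol reviewed here.

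**The concern.** The two documents give the same patient different outcomes. Under the protocol, a death or progression that follows two missed scans is an event on the day it is documented. Under the SAP it is not an event at all, and follow-up is cut back to the last valid scan. This goes beyond adding detail to the protocol, because it turns a protocol-defined event into a censored observation.

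Both plans are tied to the same amendment, so a difference in versions does not explain the gap. Section 9.1 is where the SAP should declare such a departure, and it declares none. The report would then present PFS and DOR as the protocol-defined endpoints when they are not. In advanced disease, missed scans may reflect deterioration, so the extra censoring may also be informative.

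**Working it through.** The documents give no PFS or DOR median, event count, power or missed-scan rate, so there is no planned figure to reproduce. The check has three parts.

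**1. One assumed patient under both rules.** The patient has valid scans at the first two visits, misses the next two, then dies half an interval after the second missed scan without new therapy. Scan intervals are from Protocol Section 11.3. Day = 7 × weeks + 1, with fractions of a day dropped.

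| Schedule | Last valid scan | Death | Protocol 15.4 | SAP Table 4 |
|---|---|---|---|---|
| 8-weekly (Parts 1a, 2) | week 16: 7 × 16 + 1 = day 113 | week 36: 7 × 36 + 1 = day 253 | event, day 253 | censored, day 113 |
| 9-weekly (Parts 1b, 3) | week 18: 7 × 18 + 1 = day 127 | week 40.5: 283 + 1 = day 284 | event, day 284 | censored, day 127 |

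The protocol's own censoring triggers (study termination, analysis cutoff, confounding therapy) do not apply to this patient.

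**2. How many patients could change status.** The inputs to this simulation are assumptions. Scans are 9-weekly; time to deterioration is exponential with median 13 weeks; 10%, 20% or 30% of patients stop scanning at deterioration and die a median of 22 weeks later. Patients who keep scanning have their event at the next scan. The protocol rule counts the death. The SAP rule censors at the last scan if at least two scheduled scans fall between that scan and death.

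| Share who stop scanning | Switched, all deaths captured | In a cohort of 26 | Switched, deaths captured to day 97 only | In a cohort of 26 |
|---|---|---|---|---|
| 10% | 6.5% | 26 × 0.065 = 1.7 | 0.2% | 26 × 0.002 = 0.05 |
| 20% | 13.0% | 26 × 0.130 = 3.4 | 0.5% | 26 × 0.005 = 0.13 |
| 30% | 19.5% | 26 × 0.195 = 5.1 | 0.7% | 26 × 0.007 = 0.18 |

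The lower bound assumes that treatment stops at deterioration and that deaths are known only within the safety follow-up of Protocol Section 11.5.1 (90 to 97 days in Parts 1b and 3). On the 8-week monotherapy schedule the window is 37 days, or 37/7 = 5.3 weeks. Deterioration falls less than 8 weeks after the last scan, so a captured death falls less than 8 + 5.3 = 13.3 weeks after it. Two missed scans need 16 weeks, so no patient switches.

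**3. Which way PFS moves.** In the same model with all deaths captured, 27-week PFS is about 28% under the protocol against 26% under the SAP, then 33% against 28%, and 37% against 30%. The SAP rule gives the lower figure each time. With deaths captured to day 97 only, the two rules differ by at most 0.1 percentage points.

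A second illustration uses 26 patients, exponential PFS, 8-weekly scans and 4,000 runs. In it, 30% of events are documented only after two missed scans. The SAP event count falls from 26 to 26 × 0.7 = 18.2. The mean Kaplan-Meier median, over runs where the median is reached, is:

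| Assumed true median | Protocol rule | SAP rule |
|---|---|---|
| 8 weeks | 17.8 weeks | 14.8 weeks |
| 16 weeks | 25.7 weeks | 26.8 weeks |
| 24 weeks | 32.9 weeks | 38.6 weeks |

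The sign of the difference changes with the assumed median. If no event follows two missed scans, the rules agree exactly.

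**The case against.** The other side has several fair points.

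- **The rule is printed, not hidden.** Table 4 states it and names its source, and censoring after missed assessments is a recognised convention. This stands. What is missing is the declaration in Section 9.1.
- **Late deaths may rarely be recorded.** Protocol Section 11.5 has no survival follow-up (Attachment 10 records its removal), and safety contact ends at 37 or 97 days. This largely stands and is why the lower bound is shown. However, disease-status follow-up in Section 11.5.2 runs until death, among other endpoints, so some late events can reach the database.
- **Little depends on these endpoints.** SAP Section 3.2 calls all analyses exploratory, and PFS and DOR have no hypothesis or decision rule. Simon cohorts reach 25 to 34 patients only if Stage 2 opens; Stage 1 has 10 to 13. DOR covers responders only: at the 15% target, 26 × 0.15 = 3.9 patients, and at the 2% background rate, 26 × 0.02 = 0.5. SAP Section 7.3.4 omits the Kaplan-Meier analysis when responders are very few. This stands and limits the severity.
- **Another row of Table 4 counts death before the first progressive assessment as an event.** This does not remove the conflict. A death after missed scans with no earlier progression also precedes any progressive assessment, so the missed-scan row could never apply to deaths unless it overrides that row.

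A reader might infer that the SAP rule flatters the drug by removing events. The documents do not support that: 27-week PFS was lower under the SAP rule in one illustration, and the median moved both ways in the other. A reader might also take 2 to 5 reclassified patients per 26 as an estimate. That is the upper bound, and it requires every late death to be captured.

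**Conclusion.** Wrong as written, minor severity. For a patient who misses two scans and then dies or progresses without new therapy, Protocol 15.4 and SAP Table 4 give opposite outcomes for PFS, and for DOR if that patient is a responder. The not-applicable entry in SAP Section 9.1 is therefore incorrect. This conclusion rests on the text alone and needs no simulation.

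The number of patients affected and the direction of the shift cannot be derived from the documents. Under the assumptions shown, between under 1% and about 6-20% of patients change status. Both bounds leave out new anticancer therapy, which leads to censoring under either rule. The effect is confined to descriptive medians, intervals and Kaplan-Meier curves. The Simon response decisions, sample size and type I error are untouched.

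It might also be inferred that the protocol rule has to be the main one. The documents do not show which rule is less biased, so either choice is defensible if it is declared.

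**What to change.** Choose one rule as the main analysis and apply it to both PFS and DOR.

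- If the Table 4 rule is kept, replace the entry in SAP Section 9.1 with a declared departure from Protocol 15.4 and its rationale. Report the protocol definition as a sensitivity analysis.
- If the protocol rule is chosen, change the missed-assessment row of Table 4 so that documented progression or death remains an event. Report the missed-scan censoring as a sensitivity analysis.
- In either case, state for each cohort how many patients are classified differently. Readers can then see whether the choice mattered.

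The cost is a revision of the SAP wording and one extra run of the PFS and DOR programs. No new data are needed.
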